1.2. Rationale for the Study

The research data available to date indicate that SCB01A is a promising anti-cancer agent with vascular disrupting activity that has potential for treatment of various malignancies, particularly for patients with drug resistance to existing therapies. The drug has been trialed in human subjects in dose-escalation phase I study, and maximum tolerated dose (MTD) is 24 mg/m² (each cycle consists of one intravenous [i.v.] administration of SCB01A via a central line every 3 weeks). In the phase I study, partial response (PR) (shrinkage of tumor size to 50%) was observed in cycle 9 (3 mg/m²) of one subject with right buccal squamous cell carcinoma and disease stabilization lasted for 14 cycles. Summary from current clinical findings note a total of 19/33 (57.6%) subjects had stable disease (SD) for at least 2 cycles. Extended disease stabilizations were especially observed for 23 cycles in one subject with cholangiocarcinoma (4 mg/m²) and 15 cycles in one subject with rectal cancer (3 mg/m²) respectively, suggested that the most prominent SD subjects remain in low dose (less than 6.5 mg/m²).

Pre-clinical study of SCB01A showed that the concentrations at which tubulin inhibition occurred were around 80 nM for 24-hour exposure or 200 nM for 6-hour exposure. However, pharmacokinetic (PK) results of both phase I study and an ongoing phase II study showed that the average elimination half-life (t_{1/2}) of a 3-hours i.v. infusion of SCB01A is approximately 2.5 hours and almost no SCB01A can be detected after 10 hours, indicating most subjects were treated in short API exposure time and may have been insufficient to achieve efficacy. Furthermore, clinical experiences demonstrated that extended infusion duration may reduce susceptible chemotherapy induced adverse reaction especially peripheral neuropathy (JCO 1999, 17(11): 3403-11). Summary from both efficacy and safety evidences suggesting that to extend the cumulative exposure duration of SCB01A beyond effective concentration in blood may be benefit to patient's best interest.

Two phase I clinical studies were performed "A Phase 1 Dose Escalation Study of SCB01A in Subjects with Advanced Solid Tumors Who Have Failed Standard Therapy" and "Long-Term Compassionate Use Study for Continued Administration of SCB01A in Subjects Who Completed Treatment With SCB01A in the Previous Protocol #SCB01A-01" respectively. The phase I study demonstrated that SCB01A has encouraging safety and efficacy and support for further Phase II study. 33 subjects were enrolled in the study and 31 subjects completed the main treatment. Among the 31 subjects, 11 of them completed the extension treatment of SCB01A. Up to date, 5 subjects, two in main and extension period respectively, experienced 7 SUSAR events. (Including gastric ulcer bleeding, thrombocytopenia, cough, radiation recall dermatitis, thromboembolic event, muscle weakness lower limb, and sepsis). In addition, 5 dose limiting toxicities and 61 adverse reactions were reported in this study.

The aim of this Phase II study with SCB01A is to determine the efficacy and safety of SCB01A in subjects with squamous cell carcinoma of head and neck who have failed previous platinum based therapies.

2. Study Objectives

This is a Phase II study with intra-subject dose escalation to evaluate the efficacy and safety of SCB01A in subjects with recurrent or metastatic squamous cell carcinoma in head and neck.

2.1. Primary Objective

To assess the objective response rate (ORR) according to the Response Evaluation Criteria in Solid Tumors (RECIST) version 1.1.

2.2. Secondary Objective

The secondary objectives of the study are listed below:

- To evaluate the safety and toxicity profile of SCB01A.
- To assess the overall survival (OS) after first treatment with SCB01A.
- To assess the progression-free survival (PFS).
- To assess the best overall tumor response after treatment with SCB01A.
- To assess the PK profile.

3. Investigational Plan

3.1. Description of Overall Study Design and Plan

[figure not shown]
This study is a multicenter, open-label, Phase II trial. The study will be conducted in two stages:

- **Stage I:** A total of up to 10 evaluable subjects will be enrolled for Stage I to receive at least 3 cycles of i.v. administration by 24-hours infusion of SCB01A under intra-subject dose escalation regimen. The tumor response review will be performed with the subjects who completed at least 3 cycles of SCB01A treatment. If at least one response (CR or PR) is observed, another 19 evaluable subjects will be enrolled into Stage II.
- **Stage II:** 19 evaluable subjects will be enrolled at stage II and treated with the same intra-subject dose escalation regimen from starting dose 12 mg/m². The tumor response review will be performed with the subjects who completed 3 cycles of SCB01A treatment.

Intra-Subject Dose Escalation

All subjects enrolled in this study will be treated from the same starting dose 12 mg/m² (Dose 1) given on Days 1 and 8 in a 21-day cycle by 24 h IV infusion. If the subject experiences no dose-limiting toxicity (DLT) during the period, dose escalation of SCB01A to 18 mg/m² (Dose 2) occurred from cycle 2; and increased to 24 mg/m² (Dose 3) on cycle 3 ([Figure 1](#)).

Figure 1: Intra-Subject Dose Escalation Plan

[figure not shown]
Dose Modification

If the subject experiences a DLT at a given dose level, dose escalation will be halted and a reduced dose will be given to the subject. Dose adjustments were allowed based on the toxicity, efficacy evaluation, and clinical judgment by physician.

Rules for dose modifications of the study ([Figure 2](#)) are listed as following:

1. Dose 1 (12 mg/m²), will be the starting dose regimen for all subjects. Safety and clinical benefit observation will be performed prior to drug administration on Cycle 2 Day 1.
 - a) Dose de-escalation: if any DLT experienced before Cycle 1 Day 8, the dose will be de-escalated to Dose 1a (9 mg/m²) for Cycle 1 Day 8. If first DLT during Cycle 1 is experienced after Cycle 1 Day 8, the dose will be de-escalated to Dose 1a (9 mg/m²) for Cycle 2. If no DLT is observed in Dose 1a, the subjects will receive the Dose 1a until PD, consent withdraw or death.

- Once more dose de-escalation (Dose 1b, 7 mg/m²) will be allowed if another DLT is observed in Dose 1a.
- b) Dose maintained: If clinical benefit observed at Dose 1 and without DLT, the dose level can be maintained until PD, intolerable toxicity, consent withdraw or death.
2. Dose 2 (18 mg/m²), will be administrated for one cycle and safety and clinical benefit observation will be performed prior to drug administration on Cycle 3 Day 1.
- a) Dose de-escalation: if any DLT experienced before Cycle 2 Day 8, the dose will be de-escalated to Dose 2a (15 mg/m²) for Cycle 2 Day 8. If first DLT during Cycle 2 is experienced after Cycle 2 Day 8, the dose will be de-escalated to Dose 2a (15 mg/m²) for Cycle 3. If no DLT is observed in Dose 2a, the subjects will receive the Dose 2a until PD, consent withdraw or death. Once more dose de-escalation (Dose 2b, 12 mg/m²) will be allowed if another DLT is observed in Dose 2a.
- b) Dose maintained: If clinical benefit observed at Dose 2 and without DLT, the Dose 2 can be continued until PD, intolerable toxicity, consent withdraw or death.
3. Dose 3 (24 mg/m²), will be administrated for one cycle and safety and tumor assessment will be performed prior to drug administration on Cycle 4 Day 1.
- a) Dose de-escalation: if any DLT experienced before Cycle 3 Day 8, the dose will be de-escalated to Dose 3a (20 mg/m²) for Cycle 3 Day 8. If first DLT during Cycle 3 is experienced after Cycle 3 Day 8, the dose will be de-escalated to Dose 3a (20 mg/m²) for Cycle 3. If no DLT is observed in Dose 3a, the subjects will receive the Dose 3a until PD, consent withdraw or death. Once more dose de-escalation (Dose 3b, 16 mg/m²) will be allowed if another DLT is observed in Dose 3a.

Figure 2: Dose Modification

If the subject experienced any neurotoxic DLT, the subject will be withdrawn.

Subjects will be considered to be non-evaluable for ORR if they receive study drug for fewer than 9 weeks (3 cycles) of treatment for any reason other than study-drug related toxicity. Non-evaluable subjects will be replaced.

All subjects will be treated until the occurrence of progressive disease, intolerable adverse events (AEs)/toxicity, consent withdrawal or death. After discontinuation of study treatment, all subjects will be followed for survival and disease-specific therapies of the clinician's choice will be administered. Follow-up visits will be scheduled every 3 weeks for 9 weeks (i.e. week 3, week 6, and week 9), thereafter every 9 weeks until the end of the study.

End of study will be either 12 months after the 1st treatment with SCB01A or end of 27 weeks survival follow-up, whichever comes later.

Data and Safety Monitoring Board (DSMB)

The responsibilities of the DSMB, composed of medical monitors (physicians experienced in oncology studies) and at least one statistician, are to review and evaluate the data for safety, study conduct and progress, and make recommendations concerning the continuation, modification, or termination of study. Serial assessments of PK results also may be taken into account for safety evaluation. A neurologist will be invited to join DSMB meeting as a consultant when neurotoxicity occurred.

The document review or meeting of DSMB will be held when the following scenarios:

- A subject is not recovered from Grade 2 neurotoxicity over three weeks;
- A subject revealed Grade 3 or above neurotoxicity;
- After 10 evaluable subjects finished the study in Stage I;

The schedule of assessments is shown in detail in [Table 1](#), [Table 2](#) and [Table 3](#). The results of protocol specific assessments and procedures will be recorded in the source documents for the subjects and on the appropriate page of the case report form (CRF). The different study days are described below.

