
 • ORR is defined as the percentage of subjects who have achieved confirmed CR and PR during treatment phase, according to RECIST v1.1. Not-confirmed CR or PR, or withdraw for DLT are counted as non-responder. • PFS is defined as the time from the start of treatment up to the date of first progression based on RECIST v1.1 or the date of death, whichever comes first. • OS is defined as the time from the start of treatment up to the time that the subject is still alive. • Best overall tumor response defined as the best response from start of treatment through all treatment phase or until disease progression/recurrence. 
Survival data will be collected throughout the active treatment phase and during the 27 weeks follow-up period. Survival follow-up after subject discontinuation of treatment will be conducted every 3 weeks during the first 9 weeks, thereafter every 9 weeks until the end of the study to assess for survival. Survival rate will only be assessed in subjects with measurable disease at baseline.
 
Dose Limiting Toxicity (DLT):
 
All toxicities will be classified according to the National Cancer Institute (NCI) Common Terminology Criteria for AEs (CTCAE) version 4.03. DLT will be defined as the occurrence of any of the following criteria unless there is definitive alternative evidence that administration of SCB01A did not cause the specific toxicity:
 
 • Grade 4 neutropenia exceeding 5 days' duration; • Grade 4 thrombocytopenia; • Grade 4 anemia; • Grade 3 or greater neutropenia with complications (e.g., fever, infection etc.); • Grade 3 or greater thrombocytopenia with complications (e.g., bleeding); • Grade 3 or greater non-hematological AEs including Grade 3 unmanageable nausea and vomiting that persist for 3 or more days after drug administration. Grade 3 fatigue lasting for ≤ 1 week is not considered as a DLT; • Grade 3 or greater prolonged QTc interval; • Grade 3 or greater neurotoxicity; • Delayed treatment exceeding 14 days duration due to drug-related toxicity; • Not able to recover from grade 2 neurotoxicity exceeding 3 weeks. 
Safety measurements:
 
The following safety assessments will be done during the study:
	

Name of Sponsor/Company: SynCore Biotechnology Co. Ltd.	
Name of Study Product: SCB01A	
Protocol Number: SCB01A-22	Indication: Recurrent or metastatic squamous cell carcinoma of head and neck

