4.9. Dose Adjustment and Toxicity Management

If a study treatment-related Grade 3 or 4 AE occurs, the study treatment will be placed on hold until the event is resolved to Grade ≤ 1 or returns to baseline before resuming the study drug. If the Grade 3 or 4 event does not resolve or return to baseline within 14 days or return to Grade 3 or 4 toxicity after resuming, treatment with the study drug will cease. However the subject should be followed-up for survival analysis until the end of the study.

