6.2. Dose Limiting Toxicity (DLT)

All toxicities will be classified according to the NCI Common Terminology Criteria for AEs (CTCAE) version 4.03.

DLT will be defined as the occurrence of any of the following criteria unless there is definitive alternative evidence that administration of SCB01A did not cause the specific toxicity:

- Grade 4 neutropenia exceeding 5 days' duration
- Grade 4 thrombocytopenia
- Grade 4 anemia
- Grade 3 or greater neutropenia with complications (e.g., fever, infection etc.)

- Grade 3 or greater thrombocytopenia with complications (e.g., bleeding)
- Grade 3 or greater non-hematological AEs including Grade 3 unmanageable nausea and vomiting that persist for 3 or more days after drug administration. Grade 3 fatigue lasting for ≤ 1 week is not considered as a DLT
- Grade 3 or greater prolonged QTc interval
- Grade 3 or greater neurotoxicity
- Delayed treatment exceeding 14 days duration due to drug-related toxicity.
- Not able to recover from grade 2 neurotoxicity exceeding 3 weeks

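### On the nominal schedule the three-week Grade 2 neurotoxicity DLT cannot be met before the next dose step, so the written default raises the dose while the symptom is ongoing

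*Protocol*

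**What the plan says.** Protocol section 3.1 starts every subject at 12 mg/m² on Days 1 and 8 of a 21-day cycle. Escalation is conditional on one thing: "If the subject experiences no dose-limiting toxicity (DLT) during the period, dose escalation of SCB01A to 18 mg/m²" takes place from Cycle 2, with a further step to 24 mg/m² in Cycle 3.

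Section 6.2 lists the DLT criteria. Grade 3 or greater neurotoxicity qualifies at once. Grade 2 qualifies only under "Not able to recover from grade 2 neurotoxicity exceeding 3 weeks".

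Other provisions that bear on a Grade 2 symptom:

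- **Pre-step check (3.1).** "Safety and clinical benefit observation will be performed prior to drug administration on Cycle 2 Day 1", with a matching check before Cycle 3 Day 1. Neither states a Grade 2 threshold.
- **Physician discretion (3.1, repeated in 4.8).** "Dose adjustments were allowed based on the toxicity, efficacy evaluation, and clinical judgment by physician".
- **Maintaining the dose (3.1).** Dose 1 or Dose 2 may be continued if there is clinical benefit and no DLT.
- **Mandatory hold (4.9).** "If a study treatment-related Grade 3 or 4 AE occurs, the study treatment will be placed on hold". Grade 2 is not covered.
- **DSMB (3.1).** One trigger is "A subject is not recovered from Grade 2 neurotoxicity over three weeks", which is the same clock as the DLT.
- **Nerve conduction testing (5.9).** Grade 2 symptoms prompt a test, but its result does not alter treatment unless the symptom is judged clinically significant.
- **Consequence.** "If the subject experienced any neurotoxic DLT, the subject will be withdrawn" (3.1). In the Synopsis definition of ORR, "Not-confirmed CR or PR, or withdraw for DLT are counted as non-responder".

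The SAP pages supplied contain no dose rule.

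**The concern.** The DLT list is what section 3.1 uses to halt escalation. A criterion that needs more than 21 days of persistence cannot act on a decision taken 21 days after the cycle began. The protocol includes a Grade 2 neurotoxicity DLT, but in Cycles 1 and 2 that DLT comes too late to influence the next step.

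At stake is drug given at a dose 50% higher (18/12 = 1.50) or 33% higher (24/18 = 1.33) to a subject with ongoing Grade 2 neurotoxicity. The protocol treats this toxicity as a leading risk: two of the three DSMB triggers concern it, and a neurotoxic DLT leads to withdrawal, not to a reduced dose. Onsets in Cycle 3 or later are unaffected, because section 3.2.11 keeps the dose the same from Cycle 4.

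**Working it through.** **Inputs.** Cycle length of 21 days, infusions on Days 1 and 8, doses 12, 18 and 24 mg/m² (Protocol 3.1). Visit days and ±1-day windows (Tables 1 and 2). DLT after more than 3 weeks, taken as more than 21 elapsed days (6.2).

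**1. Reproduce the schedule.** Study day = 1 + 21 × (cycle − 1) + (cycle day − 1).

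- C2D1 = 1 + 21 + 0 = 22; C2D8 = 1 + 21 + 7 = 29
- C3D1 = 1 + 42 + 0 = 43; C3D8 = 1 + 42 + 7 = 50
- C4D1 = 1 + 63 + 0 = 64

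These match Tables 1 and 2.

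**2. When the criterion is met.** For onset on day d, it is met on day t if t − d > 21, so first on day d + 22.

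- Cycle 1 onset (d = 1 to 21): duration at C2D1 is 22 − d, or 1 to 21 days.
- Cycle 2 onset (d = 22 to 42): duration at C3D1 is 43 − d, or 1 to 21 days.

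Neither exceeds 21, so 0 of 21 onset days qualify in either cycle.

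**3. Escalated infusions given before the DLT can be declared.** The per-infusion excess over the current level is 18 − 12 = 6 or 24 − 18 = 6 mg/m².

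| Onset day | Criterion first met | Infusions at the higher dose | Excess (mg/m²) |
|---|---|---|---|
| 1–7 | 23–29 | one at 18 mg/m² | 6 |
| 8–21 | 30–43 | two at 18 mg/m² | 12 |
| 22–28 | 44–50 | one at 24 mg/m² | 6 |
| 29–42 | 51–64 | two at 24 mg/m² | 12 |

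In each cycle, 7 of 21 onset days lead to one such infusion and 14 of 21 to two.

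**4. The step after that.** For Cycle 1 onsets, d + 22 ≤ 43 for all 21 days. A symptom that persists is therefore caught by C3D1 and the subject does not reach 24 mg/m².

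**5. Sensitivity, one change at a time.**

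- *Visit one day late.* C2D1 on day 23 catches d = 1 (23 − 1 = 22 > 21). C3D1 on day 44 catches d = 22. If C2D1 was also a day early (day 21), a day-44 visit catches d = 21 and 22, the most that windows alone allow.
- *Rule read as 21 full days.* First met on d + 21, which catches only d = 1 by day 22 and d = 22 by day 43: 1 of 21 in each cycle.
- *A 14-day toxicity delay.* Section 6.2 makes only a drug-related delay over 14 days a DLT. Moving C2D1 to 22 + 14 = 36 gives d + 22 ≤ 36, so onsets on days 1 to 14 (14 of 21) qualify before the step. Delaying is the physician's choice, not a rule.

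**The case against.** The strongest reply is that the plan leaves Grade 2 toxicity to clinical judgment on purpose. A safety check is mandatory before each step, the physician may adjust the dose for toxicity, the investigator may stop treatment for an intolerable event (3.8.2), and section 5.9 contemplates a schedule change when a neurological symptom is clinically significant. A permitted delay also brings many onsets within the criterion. Escalating unless a defined DLT occurs is a coherent design, and the entry exclusion for Grade 2 neuropathy does not set an on-treatment threshold.

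Most of this stands as a limit on the point. The gap lies in the DLT criterion and the written default; it does not force anyone to be escalated. But every one of these routes is optional and none has a Grade 2 threshold, so up to four centers could treat the same case differently.

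A reader might go further and infer that the gap costs responders or biases ORR, because the subject is escalated, then withdrawn and counted as a non-responder. The documents do not support this. Withdrawal and non-responder status follow from persistence beyond three weeks and would apply equally if the dose had not been raised. Nothing in the documents shows that the extra drug makes the symptom persist. Nor would a persistent Cycle 1 onset be carried to 24 mg/m²; step 4 shows that it is blocked.

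**Conclusion.** The point holds as a gap in the written dose rules. On the nominal schedule the Grade 2 neurotoxicity DLT cannot halt the next step for onsets in Cycle 1 or Cycle 2, and no other mandatory rule in the text does so. The demonstrated effect is 6 or 12 mg/m² of extra drug during unresolved Grade 2 neurotoxicity when the default is followed. It is worth correcting because the default can be made safer with a short rule.

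This rests on four conditions:

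- more than three weeks means more than 21 elapsed days;
- visits fall on or near their nominal days;
- the physician neither adjusts, delays nor maintains the dose;
- Figures 1 and 2, which are not visible in the text, contain no additional Grade 2 rule.

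The counts are of calendar days, not subjects. Up to 37 subjects come under the rule, but no Grade 2 rate is given, so the number affected cannot be estimated.

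**What to change.** Add to the dose rules in section 3.1, the matching Synopsis text and section 4.8:

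*A subject with unresolved Grade 2 neurotoxicity at Cycle 2 Day 1 or Cycle 3 Day 1 is not escalated; the dose is no higher than the current level until recovery to Grade 1 or lower. The physician may still reduce or delay the dose. Grade 3 or greater neurotoxicity remains a DLT with withdrawal.*

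Also state whether a deferred step may be taken from Cycle 4, since section 3.2.11 keeps the dose the same from then. No new data are needed: adverse event onset and severity (7.2) and infusion times (4.13) are already recorded.

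The cost falls on affected subjects. Planned dose over Cycles 1 to 3 is 2 × (12 + 18 + 24) = 108 mg/m². With a one-cycle deferral:

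- at Cycle 2 Day 1: 2 × (12 + 12 + 18) = 84 mg/m², a fall of 24/108 = 22%;
- at Cycle 3 Day 1: 2 × (12 + 18 + 18) = 96 mg/m², a fall of 12/108 = 11%.

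This lowers dose intensity before the first response assessment. A deferred Stage I subject also loses the Cycle 3 PK sampling, which requires 24 mg/m² (5.8). Each such case is 1 of 10 to 13 Stage I subjects, or 8% to 10%.

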- a) Dose de-escalation: if any DLT experienced before Cycle 2 Day 8, the dose will be de-escalated to Dose 2a (15 mg/m²) for Cycle 2 Day 8. If first DLT during Cycle 2 is experienced after Cycle 2 Day 8, the dose will be de-escalated to Dose 2a (15 mg/m²) for Cycle 3. If no DLT is observed in Dose 2a, the subjects will receive the Dose 2a until PD, consent withdraw or death. Once more dose de-escalation (Dose 2b, 12 mg/m²) will be allowed if another DLT is observed in Dose 2a.
- b) Dose maintained: If clinical benefit observed at Dose 2 and without DLT, the Dose 2 can be continued until PD, intolerable toxicity, consent withdraw or death.
- 3. Dose 3 (24 mg/m²), will be administrated for one cycle and safety and tumor assessment will be performed prior to drug administration on Cycle 4 Day 1.
 - a) Dose de-escalation: if any DLT experienced before Cycle 3 Day 8, the dose will be de-escalated to Dose 3a (20 mg/m²) for Cycle 3 Day 8. If first DLT during Cycle 3 is experienced after Cycle 3 Day 8, the dose will be de-escalated to Dose 3a (20 mg/m²) for Cycle 3. If no DLT is observed in Dose 3a, the subjects will receive the Dose 3a until PD, consent withdraw or death. Once more dose de-escalation (Dose 3b, 16 mg/m²) will be allowed if another DLT is observed in Dose 3a.

Figure 2: Dose Modification

If the subject experienced any neurotoxic DLT, the subject will be withdrawn.

Per-protocol (PP) subjects will be considered to be evaluable for ORR conclusion; Non-evaluable subjects will be replaced.

Simon’s Two-Stage Design¹

Stage I: A total of up to 10 evaluable subjects will be enrolled for Stage I to receive at least 3 cycles of i.v. administration by 24-hours infusion of SCB01A. The tumor response review will be

Name of Sponsor/Company: SynCore Biotechnology Co. Ltd.	
Name of Study Product: SCB01A	
Protocol Number: SCB01A-22	Indication: Recurrent or metastatic squamous cell carcinoma of head and neck

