3.2.11. Cycle 4, Days 1 and 8 (C4D1 and C4D8)

If the subject, per the investigator's discretion, is experiencing clinical benefit, they may continue with treatment of SCB01A at the same dose until the study is terminated. The assessments on Days 1 and 8 will continue to be the same as for Cycle 2, Day 1 and Day 8 (see [Section 3.2.5](#) and [3.2.6](#), respectively) with the exception that ECG will only be performed prior to study drug administration (pre-infusion, 0 hr), and then at the end of the infusion (24 hr) on Days 1 and 8 of additional treatment cycles beyond Cycle 3.

Tumor assessment should be performed at baseline, and at the end of every 3 cycles which needs to be arranged within 4 days prior to the next cycle.

Note: No Day 15 visit starting from Cycle 4.

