4.8. Selection and Timing of Dose for each Subject

The selection and timing of dose for each subject is described in [Section 3.1](#).

Subjects entered into Stage I and II will be allocated Dose 1, 2 and 3 under intra-subject dose escalation regimen. If the subject experiences a DLT at a given dose level, dose escalation will be halted and a reduced dose will be given to the subject. Dose adjustments were allowed based on the toxicity, efficacy evaluation, and clinical judgment by physician.

Dose 1: One i.v. administration of 12 mg/m² SCB01A on Days 1 and 8 of a Cycle 1;

Dose 1a: one i.v. administration of 9 mg/m² SCB01A
Dose de-escalation (if any DLT experienced during Dose 1)

Dose 1b: one i.v. administration of 7 mg/m² SCB01A
Dose de-escalation (if any DLT experienced during Dose 1a)

Dose 2: One i.v. administration of 18 mg/m² SCB01A on Days 1 and 8 of a Cycle 2;

Dose 2a: one i.v. administration of 15 mg/m² SCB01A
Dose de-escalation (if any DLT experienced during Dose 2)

Dose 2b: one i.v. administration of 12 mg/m² SCB01A
Dose de-escalation (if any DLT experienced during Dose 2a)

Dose 3: One i.v. administration of 24 mg/m² SCB01A on Days 1 and 8 of a Cycle 3;

Dose 3a: one i.v. administration of 20 mg/m² SCB01A
Dose de-escalation (if any DLT experienced during Dose 3)

Dose 3b: one i.v. administration of 16 mg/m² SCB01A
Dose de-escalation (if any DLT experienced during Dose 3a)

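### Rule 3a reduces the dose for a late Cycle 3 DLT in a cycle with no dose left, and Sections 3.1 and 4.9 disagree on reducing or stopping after a returning or unresolved Grade 3/4 toxicity

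*Protocol*

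**What the plan says.** Protocol Section 3.1 (Dose Modification) sets a general rule for a DLT: "dose escalation will be halted and a reduced dose will be given to the subject". Three parallel rules then say when the reduction starts if the first DLT of a cycle comes after Day 8:

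- Rule 1a: "experienced after Cycle 1 Day 8, the dose will be de-escalated to Dose 1a (9 mg/m²) for Cycle 2".
- Rule 2a: "experienced after Cycle 2 Day 8, the dose will be de-escalated to Dose 2a (15 mg/m²) for Cycle 3".
- Rule 3a: "experienced after Cycle 3 Day 8, the dose will be de-escalated to Dose 3a (20 mg/m²) for Cycle 3".

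The synopsis words rule 3a the same way: "during Cycle 3 is experienced after Cycle 3 Day 8, the dose will be de-escalated to Dose 3a (20 mg/m²) for Cycle 3". Rule 3a goes on to say that, if the reduced dose brings no DLT, "the subjects will receive the Dose 3a until PD, consent withdraw or death". Section 4.8 lists Dose 3a as the reduction after a DLT at Dose 3 but does not say when it starts. On Cycle 4, Section 3.2.11 says of subjects with clinical benefit that "they may continue with treatment of SCB01A at the same dose until the study is terminated". It makes no exception for a subject who has had a DLT.

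Each of the three rules also permits one further reduction (to Dose 1b, 2b or 3b) if another DLT occurs at the first reduced level. A neurotoxic DLT leads to withdrawal instead.

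Section 4.9 deals with treatment-related Grade 3 or 4 adverse events. Study drug is held until recovery. It is ended for good if the event has not settled within 14 days, or if Grade 3 or 4 toxicity comes back once dosing has restarted. Section 6.2 makes a drug-related treatment delay of more than 14 days a DLT in its own right.

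**The concern.** Rule 3a ties a reduction to a cycle in which every dose has already been given. The only text that addresses the Cycle 4 dose by name keeps it unchanged. This happens at the highest planned dose level, 24 mg/m², which Section 1.2 gives as the phase I maximum tolerated dose for one administration every 3 weeks.

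Sections 3.1 and 4.9 can both apply to the same subject with the same toxicity. One allows treatment to continue at a lower dose and the other ends it. Neither refers to the other. Two sites, each following the protocol, could therefore treat the same subject differently after a serious toxicity.

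That is first a matter of subject safety. It can also reach the primary endpoint. The synopsis and SAP Section 9.8 score a subject withdrawn for DLT as a non-responder, while a subject who continues at a reduced dose can still have a response confirmed. Per-protocol membership depends partly on withdrawal for DLT (synopsis; SAP Section 9.7.1.1), and safety is tabulated by dose (Section 8.4). The decision limits are small counts, at least 1 response in 10 and at least 4 in 29, so the status of one subject can matter.

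**Working it through.** **Part 1: can rule 3a be carried out?**

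Inputs: dosing on Days 1 and 8 of a 21-day cycle (Section 3.1); C3D1 = Day 43 and C3D8 = Day 50 ± 1 (Table 1); C4D1 = Day 64 ± 1 (Table 2).

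Day 1 of cycle *c* is 1 + 21(*c* − 1), and Day 8 is seven days later.

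| Cycle | Day 1 | Day 8 | Doses left in the cycle after Day 8 | Next infusion | Cycle named for a late DLT |
|---|---|---|---|---|---|
| 1 | 1 | 8 | 0 | Day 22 (Cycle 2) | Cycle 2 |
| 2 | 22 | 29 | 0 | Day 43 (Cycle 3) | Cycle 3 |
| 3 | 43 | 50 | 0 | Day 64 (Cycle 4) | Cycle 3 |

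Rules 1a and 2a name the cycle that holds the next infusion. Rule 3a does not.

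- Days of Cycle 3 after C3D8: Days 51 to 63, or 63 − 50 = 13 days.
- Share of the cycle: 13/21 = 62%. This is a share of calendar days, not of subjects or of risk.
- Gap from C3D8 to the next infusion: 64 − 50 = 14 days. With the visit windows it runs from 63 − 51 = 12 to 65 − 49 = 16 days.

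**Part 2: reduce or stop?**

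| Event (treatment-related, not neurotoxic) | Sections 3.1 and 6.2 | Section 4.9 |
|---|---|---|
| Grade 3/4 DLT that returns at Dose 1a, 2a or 3a | One more reduction permitted (1b, 2b or 3b) | Treatment ends |
| Grade 3/4 event unresolved within 14 days that delays treatment by more than 14 days | A DLT, so the general rule gives a reduced dose | Treatment ends |

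Extent of the overlap across the ten DLT criteria in Section 6.2:

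- Seven are Grade 3 or higher by definition and are not the neurotoxicity criteria: prolonged Grade 4 neutropenia, Grade 4 thrombocytopenia, Grade 4 anemia, complicated Grade 3+ neutropenia, complicated Grade 3+ thrombocytopenia, Grade 3+ non-hematological events, and Grade 3+ QTc prolongation. If the same related event returns, both sections apply with different outcomes.
- One, the delay of more than 14 days, overlaps only when the causing event is Grade 3 or 4.
- Two, the neurotoxicity criteria, do not overlap, because Section 3.1 itself withdraws the subject.

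Check: 7 + 1 + 2 = 10.

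There is no conflict for a first DLT that settles within 14 days (hold under 4.9, then restart lower under 3.1), for a second DLT of a different kind if 4.9 is read event by event, or for a delay caused by lower-grade toxicity.

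**The case against.** On Part 1, the intention is fairly clear. The general DLT rule, the continuation sentence in rule 3a, Section 4.8 and the pattern of rules 1a and 2a all point to a reduction, and after C3D8 only one next infusion date exists. Section 3.2.11 can be read as a general continuation statement that does not override a specific DLT rule. Figure 2 is not reproduced in the available text, so what sites saw there cannot be checked. This stands as evidence of intent. It does not make the written cycle workable, and this is an operative dosing instruction that appears twice.

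On Part 2, the further reduction in Section 3.1 is a permission, whereas the stop in Section 4.9 is mandatory, and a permission can coexist with a stopping condition. Section 3.1 also ends treatment for intolerable toxicity and leaves room for clinical judgment. For an unresolved event, Section 4.9 could be read as deciding whether dosing restarts and Section 3.1 as deciding at what level. The delay cannot begin before the event that causes it, so the 14-day limit in 4.9 is normally reached no later than the delay criterion in 6.2. These readings are reasonable, and they make the unresolved-event limb weaker than the returning-event limb. But no section states them, and a site could equally read Section 3.1 as governing every DLT.

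On the endpoint, Section 4.9 ends study drug but keeps the subject in survival follow-up, and the documents do not say that this equals withdrawal for DLT. A late Cycle 3 DLT also comes after all Cycle 3 doses, with the first on-treatment tumor assessment due before C4D1. The effect on response coding is therefore possible, not shown.

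**Conclusion.** The concern holds in both parts.

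1. Rule 3a, as written in Section 3.1 and the synopsis, cannot be carried out for a first DLT on Days 51 to 63. Section 3.2.11 points the other way for Cycle 4.
2. Sections 3.1 and 4.9 are an unreconciled contradiction for related, non-neurotoxic Grade 3/4 DLTs that return after dosing restarts and, less sharply, for those unresolved within 14 days. Seven of ten DLT criteria are exposed when the same event returns, one more conditionally, and all three second reduction steps are involved in that situation.

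The conclusion rests on the nominal visit calendar and on the text alone. The documents give no DLT rates by type or recurrence, so the number of subjects affected, and any effect on the response count, cannot be estimated. It must be fixed because the ambiguity concerns whether a subject with serious toxicity is treated again.

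**What to change.** Reconcile the synopsis dose-modification and DLT text with Sections 3.1, 3.2.11, 4.8, 4.9 and 6.2, so that:

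- rule 3a names a cycle in which the instruction can be carried out, and Section 3.2.11 agrees with it for subjects who have had a DLT;
- Sections 3.1, 4.9 and 6.2 give one outcome for a returning or unresolved related Grade 3/4 toxicity, or state which section takes precedence.

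The clinical choice belongs to the sponsor and investigators, and none is proposed here.

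The SAP is written largely in the past tense and already reports subjects not evaluated for response, so dosing may be complete. In that case the clinical study report should list each subject with a late Cycle 3 DLT or with a returning or unresolved Grade 3/4 toxicity. For each it should state which section was applied and how the subject was classified for response and for the per-protocol population. Section 9.10.2 already places changes in study conduct or analysis in that report.

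Cost: an amendment to the wording and a note to sites or, after dosing, a short statement per affected subject. No extra patients or procedures are needed.
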